4.1.6.2 Presentation

Disease characteristics are summarised on the FAS in a similar manner to that described for baseline demographics (see Section 4.1.4.2).

4.1.7 Medical History and Concomitant Disease

4.1.7.1 Definitions and Derivations

Medical history information can be directly obtained from the eCRF. In case of a partial diagnosis date, if both the month and the year are available then the 1st is imputed for the day. If only the year is available, 1st January is imputed.

4.1.7.2 Presentation

Medical history is summarised by System Organ Class (SOC) and Preferred Term (PT) assigned to the event by the Medical Dictionary for Regulatory Activities (MedDRA) dictionary using frequency counts and percentage of participants in the FAS. For each PT, the number and percentage of participants reporting at least one occurrence are presented, i.e., multiple occurrences of a medical history for a participant are counted only once.

Specific surgical histories such as bronchial thermoplasty in the last 12 months are summarised by SOC and PT, separately from medical history.

4.1.8 Prior and Concomitant Medications

4.1.8.1 Definitions and Derivations

Medications taken by any participant at any time during the study are coded using the ATC classification system within the WHO Drug Dictionary. Medications are categorised for analysis according to their onset and end dates.

Prior medications are defined as those which stopped before first dose of IP. Concomitant medications are defined as those which either started or continued after first dose of IP. Concomitant medications are also defined on-treatment and off-treatment period as follows:

On-treatment period concomitant medication:

- end date ≥ date of first dose of IP and start date ≤ earliest(date of last dose of IP + 33 days; date of death, date of study withdrawal), or
- end date ongoing and start date ≤ earliest(date of last dose of IP + 33 days, date of death, date of study withdrawal)

Off-treatment period concomitant medication:

• start date > date of last dose of IP + 33 days

If a medication started and stopped at the date of first IP dose, it is considered as concomitant.

Disallowed medications include medications defined as prohibited according to CSP Section 6.5. Disallowed medications include prohibited and restricted drugs; restricted drugs are considered a disallowed medication depending on timing of use, or if there are changes in dose and regimen during the study as defined in the CSP. They will be defined following a physician review (prior to primary database lock) of the unique combinations of ATC code classifications and generic terms captured.

The handling of partial/missing dates for prior/concomitant medications is detailed in Appendix A.

4.1.8.2 Presentation

The number and percentage of participants receiving each medication (by generic term within ATC code) is presented for the FAS. Separate tables are presented for all medications received during each of the following periods: prior, concomitant (on-

treatment), concomitant (post-treatment) as defined in Section 4.1.8.1. Similar tables are presented for subjects who took disallowed concomitant medications.

The number and percentage of participants receiving systemic corticosteroids during the on-treatment period is summarised by route of administration.

Table for maintenance medications (started prior to the first day of IP) are produced displaying the baseline total daily dose categories (medium/high) of ICS medications (CSP Appendix I). The number of subjects using other maintenance asthma medications at baseline is also summarised. This summary is also presented for the interim analysis on the FAS.

Percentages are calculated relative to the number of subjects in the FAS.

4.1.9 Study Drug Compliance

4.1.9.1 Definitions and Derivations

Treatment compliance is calculated as follows:

Treatment compliance (%) = (Total number of actual dosing occasions / total number of expected dosing occasions) x 100%

To allow a participant who discontinues IP early in the compliance calculation, the total expected dosing occasion is calculated as the number of expected dosing occasions up to and including the last available dosing occasion for that participant.

4.1.9.2 Presentation

Study treatment compliance is summarised using the FAS.

The number of participants with IP administration impacted by global/country situation, including consecutive missed doses, is summarised. In addition, the number of IP doses administered by location (home, other) is summarised.

4.2 Endpoint Analyses

This section covers details related to the endpoint analyses such as primary, secondary and other endpoints. No sensitivity analysis is planned for this study. A supportive analysis is planned for primary endpoints.

An interim analysis may be performed as detailed in Section 5 with approximatively 50 participants completing V4 before the data cut-off. As the study duration for those participants is shorten than the primary analysis evaluation at Week 28, the derivation and/or presentation of OCS-related endpoints have to be adjusted. No changes to the

strategies of handling intercurrent events were introduced. Details are provided in specific sections of the SAP.

Endpoint	Popula tion	Intercurrent event strategy	Population level summary (analysis)	Details in section
Primary objective: To assess the ability of tezepelumab control ^a in adult participants with OCS-dependent asthma	ab 210 mg na	Primary objective: To assess the ability of tezepelumab 210 mg subcutaneous (SC) to reduce the prescribed OCS dose (≤ 5 mg/day) without loss of asthma control ^a in adult participants with OCS-dependent asthma	ay) without loss of a	sthma
Proportion of participants who discontinued OCS without loss of asthma control ^a at Week 28 and Week 52	FAS	 Treatment discontinuation, change in background therapy^b (other than OCS): all data included in the analysis Initiation of therapy with another biologic for treatment of asthma: final dose for analysis is defined as last reported OCS 	Proportion of participants with 95% CI	4.2.1
Proportion of participants who reduced daily prescribed maintenance OCS dose to \leq 5 mg/day without loss of asthma control ^a at Week 28 and Week 52		dose received by participant with asthma stability verified, achieved prior to initiation of another biologic.		
Secondary objective: To assess the ability of tezepelur OCS dose reduction	nab 210 m	Secondary objective: To assess the ability of tezepelumab 210 mg SC to prevent asthma exacerbations in adult participants with OCS-dependent asthma while OCS dose reduction	CS-dependent asth	ma while
The AAER over 28 weeks and over 52 weeks	FAS	- Treatment discontinuation, change in background therapy ^b	AAER with	4.2.1.8
Rate of asthma exacerbation associated with hospitalisation or emergency room (ER) visit over 28 weeks and over 52 weeks		(other than OCS): all data included in the analysis - Initiation of therapy with another biologic for treatment of asthma: only data collected up until the initiation of the other	95% CI	4.2.3
Rate of asthma exacerbation associated with hospitalisation over 28 weeks and over 52 weeks		biologic treatment is included in the analysis.		
Proportion of participants who did not experience an exacerbation over 28 weeks and over 52 weeks			Proportion of participants with	4.2.4
Proportion of participants who did not experience an exacerbation associated with hospitalisation or ER visit over 28 weeks and 52 weeks			95% CI	
Proportion of participants who did not experience an exacerbation associated with hospitalisation over 28				

weeks and over 52 weeks

Endpoint	Popula tion	Intercurrent event strategy	Population level summary (analysis)	Details in section
Secondary objective: To assess the ability of tezepelur	mab 210 m	Secondary objective: To assess the ability of tezepelumab 210 mg SC to allow reduction of the prescribed OCS dose without loss of asthma control ^a	of asthma controla	
Proportion of participants with \geq 50% reduction from baseline in daily maintenance OCS dose at Week 28 and Week 52	FAS	Same intercurrent event strategies as for primary objective.	Proportion of participants with 95% CI	4.2.5
Categorised percent reduction from baseline in the daily maintenance OCS dose at Week 28 and Week 52				4.2.6
Absolute and percent change from baseline in daily maintenance OCS dose at Week 28 and Week 52		Same intercurrent event strategies as described for secondary objective related to exacerbation.	Least Square (LS) mean with 95% CI	4.2.7
Secondary objective: To assess the ability of tezepelumab to improve lung function	mab to imp	rove lung function		
Change from baseline in post-BD FEV ₁ at Week 28 and Week 52	FAS	Same intercurrent event strategies as described for secondary objective related to exacerbation.	LS mean with 95% CI	4.2.8
Secondary objective: To assess the ability of tezepelumab to improve asthma control ^a	mab to imp	rove asthma control ^a		
Change from baseline in Asthma Control Questionnaire 6 (ACQ-6) at Week 28 and Week 52	FAS	Same intercurrent event strategies as described for secondary objective related to exacerbation.	LS mean with 95% CI	4.2.9
Secondary objective: To assess the ability of tezepelumab to improve asthma related quality of life	mab to imp	rove asthma related quality of life		
Change from baseline in standardised Asthma Quality of Life Questionnaire for 12 years and older (AQLQ[s]+12) total score at Week 28 and Week 52	FAS	Same intercurrent event strategies as described for secondary objective related to exacerbation.	LS mean with 95% CI	4.2.10
Change from baseline in St. George's Respiratory Questionnaire (SGRQ) total score at Week 28 and Week 52				4.2.11

Endpoint	Popula tion	Intercurrent event strategy	Population level summary (analysis)	Details in section
Exploratory objective: To describe changes from baseline in biomarker levels	line in bio	narker levels		
Change from baseline in biomarker levels at Week 28 and Week 52	FAS	Same intercurrent event strategies as described for secondary objective related to exacerbation.	Unadjusted mean and standard deviation (SD)	4.2.12
Exploratory objective: To assess the ability of tezepel	umab 210	Exploratory objective: To assess the ability of tezepelumab 210 mg SC to allow reduction of the prescribed OCS dose without loss of asthma controla	s of asthma control	
Time to 50% reduction of OCS dose at Week 28 and Week 52	FAS	Same intercurrent event strategies as described for secondary objective related to exacerbation.	Kaplan-Meier estimates	4.2.13
Time to 100% reduction of OCS dose at Week 28 and Week 52				
Exploratory objective: To describe the occurrence of AI	AI			
Proportion of participants with normal, partial, complete AI at Week 28 and Week 52	FAS	Same intercurrent event strategies as described for secondary objective related to exacerbation.	Proportion of participants with 95% CI	4.2.14
Exploratory objective: To assess the ability of tezepelumab to improve asthma control ^a	umab to in	prove astluna control ^a		
Proportion of ACQ-6 responders at Week 28 and Week 52	FAS	Same intercurrent event strategies as described for secondary objective related to exacerbation.	Proportion of participants with 95% CI	4.2.15
Exploratory objective: To assess the ability of tezepelumab to improve asthma related quality of life	umab to in	prove asthma related quality of life		
Proportion of AQLQ(s)+12 responders at Week 28 and Week 52	FAS	Same intercurrent event strategies as described for secondary objective related to exacerbation.	Proportion of participants with	4.2.16
Proportion of SGRQ responders at Week 28 and Week 52			95% CI	4.2.17

Endpoint	Popula tion	Intercurrent event strategy	Population level summary (analysis)	Details in section
Exploratory objective: To describe the ability of tezepe	elumab to	ezepelumab to improve Asthma Impairment and Risk Questionnaire (AIRQ)		
Change from baseline in AIRQ at Week 52	FAS	Same intercurrent event strategies as described for secondary objective related to exacerbation.	Unadjusted mean and SD	4.2.18
Proportions of AIRQ responders at Week 52			Proportion of participants with 95% CI	
Exploratory objective: To describe the ability of tezepelumab to improve Sino-nasal Outcome Test (SNOT-22)	elumab to	improve Sino-nasal Outcome Test (SNOT-22)		
Change from baseline in Sino-nasal Outcome Test (SNOT-22) at Week 28 and Week 52	FAS	Same intercurrent event strategies as described for secondary objective related to exacerbation.	Unadjusted mean and SD	4.2.19
Proportion of SNOT-22 responders at Week 28 and Week 52			Proportion of participants with 95% CI	
Exploratory objective: To describe participant satisfaction with change in daily OCS use	ion with	hange in daily OCS use		
Change from baseline in Participant Perception of OCS (PPOCS) score at Week 28 and Week 52	FAS	Same intercurrent event strategies as described for secondary objective related to exacerbation.	Proportion of participants with 95% CI	4.2.20
Exploratory objective: To evaluate the ability of tezepelumab to reduce exposure to SCS	elumab to	reduce exposure to SCS		
Mean daily exposure of systemic corticosteroids (mg/day) taken for asthma reasons over 28 and 52 weeks	FAS	Same intercurrent event strategies as described for secondary objective related to exacerbation.	Unadjusted mean and SD	4.2.21
Safety objective: To describe the safety and tolerability of tezepelumab	of tezepe	lumab		
Serious adverse events (SAEs), AE leading to discontinuation of IP (DAEs), and adverse events of special interest (AESI)	FAS	All data included in the analysis regardless of treatment discontinuation, change in background therapy ^b , or initiation of therapy with another biologic for treatment of asthma	Proportion of participants	4.6.2

^a Loss of asthma control is defined as asthma worsening or exacerbation. Asthma worsening is defined by an increase of ACQ-6 score ≥ 0.5 from baseline

^b Background therapies are collected within the CM eCRF form with Therapy reason "Disease under study".

4.2.1 Primary Endpoint - Proportion of participants who discontinue OCS, reduce OCS dose to ≤ 5 mg/day without loss of asthma control

4.2.1.1 Definition

The following primary endpoints are designed to support the primary objective of the study:

- Proportion of participants who discontinue OCS without loss of asthma control
- Proportion of participants who reduce OCS dose to ≤ 5 mg/day without loss of asthma control

Both proportions are assessed at Week 28 and at Week 52.

4.2.1.2 **Derivations**

The baseline OCS is defined in Section 3.3.1.2. The final OCS dose at Week 28 (Visit 9) or at Week 52 (Visit 15) is defined as in Section 3.3 and Table 4. Strategies of handling intercurrent events are presented in Section 4.2.

Table 4 Final daily maintenance OCS derivation

Situation	Final daily maintenance OCS dose
Initiation of therapy with another biologic for treatment of asthma	Last reported OCS dose ^a received by participant with asthma stability verified ^b prior to initiation of another biologic for treatment of asthma.
Premature withdrawal from the study	Last reported OCS dose ^a received by participant with asthma stability verified ^b at the time of study withdrawal.
Any other situation	Last reported OCS dose ^a received by participant with asthma stability verified ^b

^a daily OCS dose is based on information collected in ECSYSCRT eCRF.

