1.1 Study objectives

Table 1 Objectives and Endpoints

Objectives	Estimand description/Endpoints				
Primary objectives					
To assess the ability of tezepelumab 210 mg subcutaneous (SC) to reduce the prescribed OCS dose (≤ 5 mg/day) without loss of asthma control³ in adult participants with OCS-dependent asthma	 Proportion of participants who discontinued OCS without loss of asthma control^a at Week 28 and Week 52 Proportion of participants who reduced daily prescribed maintenance OCS dose to ≤ 5 mg/day without loss of asthma control^a at Week 28 and Week 52 Population: Adult with OCS-dependent asthma requiring high-dose ICS plus a LABA with or without additional asthma 				
	controller and with at least 1 asthma exacerbation in the prior year who received at least one dose of tezepelumab Intercurrent events: • Treatment discontinuation, change in background therapy (other than OCS): All data are included in the analysis according to treatment policy estimand. • Initiate therapy with another biologic for treatment of asthma: hypothetical strategy; final dose for analysis is defined as last reported OCS dose received by participant with asthma stability verified, achieved prior to initiation of another biologic.				

	Summary measures: Proportion of participants and corresponding 95% CI at Week 28 and Week 52		
Secondary objectives			
To assess the ability of tezepelumab 210 mg SC to prevent asthma exacerbations in adult participants with OCS-dependent asthma while OCS dose reduction	 The AAER over 28 weeks and over 52 weeks Rate of asthma exacerbation associated with hospitalisation or emergency room (ER) visit over 28 weeks and over 52 weeks Rate of asthma exacerbation associated with hospitalisation over 28 weeks and over 52 weeks Proportion of participants who did not experience an exacerbation over 28 weeks and over 52 weeks Proportion of participants who did not experience an exacerbation associated with hospitalisation or ER visit over 28 weeks and 52 weeks Proportion of participants who did not experience an exacerbation associated with hospitalisation over 28 weeks and over 52 weeks 		

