3.3.1 General Study Level Definitions

3.3.1.1 Study period definition

Efficacy analyses are based on planned treatment period, unless otherwise specified. Safety analyses are based on-treatment and/or on-study period.

- Planned treatment period: starts on the date of first dose of IP and ends on the date of the Visit 15 (Week 52) visit or earlier study withdrawal date.
- On-treatment period: starts on date of first dose of IP and ends on earliest(date of last dose of IP + 33 days, date of death, date of study withdrawal). The date of study withdrawal is the completion or discontinuation date from the DISPOSITION eCRF page, where any participant status other than "Completed" has been entered.
- On-study period (planned treatment period and follow-up): starts on the date of first dose of IP and ends on the study completion or withdrawal date.

For analysis performed at primary database lock, the planned treatment period is understood to include all data recorded starting on the date of first dose of IP up until the date of the data cut-off for the primary database lock (details regarding the DCO date and data cleaning can be found in Data Cleaning Requirements for Primary Analysis Lock Plan).

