4.2.1.5 Sensitivity Analyses of the Primary Endpoint

No sensitivity analysis.

^b Asthma stability is defined as no change in OCS dose for at least 2 consecutive weeks.

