4.2.4.1 Definition

There are three proportions to assess this secondary endpoint:

- Proportion of participants who did not experience an exacerbation,
- Proportion of participants who did not experience an exacerbation associated with hospitalization or ER visit,
- Proportion of participants who did not experience an exacerbation associated with hospitalization.
- Each of those proportion of participants (i.e., who did not experience an exacerbation; an exacerbation associated with hospitalization or ER visit; an exacerbation associated with hospitalization only) are calculated over 28 weeks and over the 52-week period.

4.2.4.2 **Derivations**

For considering a participant without any experience of exacerbation, the planned treatment period defined in Section 3.3.1.1 has to be considered. A participant is considered to have completed the planned treatment period, if the planned treatment period is greater than

- than 191 (Day 196 minus 5) for the analysis at Week 28
- 359 days (Day 364 minus 5, to account for visit windowing) for the analysis at Week 52

Participants who had no asthma exacerbations during the planned treatment period and who completed the period of interest (up to Week 28 or Week 52) without initiating another biologic are defined as exacerbation free/successful outcome [a].

Participants who did not complete the planned treatment period or initiate another biologic during the planned treatment period are defined as not having a successful outcome for this endpoint [b] [c].

Participants who completed the planned treatment period without initiating another biologic and had an asthma exacerbation are defined as not having a successful outcome for this endpoint [d].

	No asthma exacerbation	Asthma exacerbation
Completed planned treatment period without initiating another biologic	[a] Exacerbation free/successful outcome	[d] No successful outcome
Did not complete treatment period or initiate another biologic during the planned treatment period	[b] No successful outcome	[c] No successful outcome

The proportion is calculated as the number of participants with a successful outcome at Week 28/Week 52 divided by total number of participants in the FAS population.

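### Death is named neither as an intercurrent event of the primary estimand nor in SAP Table 4, so a participant who dies after holding a low OCS dose can be counted as a primary success

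*SAP*

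**What the plan says.** SAP Section 1.1 (Table 1) and Section 4.2 list the intercurrent events of the primary estimand. One entry reads: "Treatment discontinuation, change in background therapy (other than OCS): All data are included in the analysis according to treatment policy estimand". The other is the start of another biologic for asthma, handled by a hypothetical strategy. Death is not listed.

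The dose that decides success is set in SAP Section 4.2.1.2: "The final OCS dose at Week 28 (Visit 9) or at Week 52 (Visit 15) is defined as in Section 3.3 and Table 4". Table 4, which has the same structure as Table 13 of the protocol, has three rows: another biologic, "Premature withdrawal from the study" and "Any other situation". Each assigns the last reported dose with stability verified, and a table footnote explains that term: "Asthma stability is defined as no change in OCS dose for at least 2 consecutive weeks".

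Section 3.3 makes the FAS the denominator. It also leaves OCS given for an exacerbation or for asthma worsening out of the maintenance dose. Section 4.2.1.3 plans no imputation and Section 4.2.1.5 no sensitivity analysis. The supplementary on-treatment analysis in Section 4.2.1.6 again uses a last stable dose for anyone who withdraws or stops treatment.

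**The concern.** After a death there is no Week 28 or Week 52 dose to estimate, yet the derivation still supplies one. If the dose that the participant had held was low enough, it counts as having stopped OCS, or reduced it to 5 mg/day or less, without loss of asthma control. The worst outcome of a taper would then be reported as its best. The same final dose feeds the 50%-or-more reduction (Section 4.2.5.2) and the categorised reduction (Section 4.2.6.2).

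The event is foreseeable. Protocol Section 2.1 describes adrenal crisis as potentially life-threatening, and Protocol Section 8.3.6 makes it an event of special interest. The SAP names death in the on-treatment period (3.3.1.1) and in time at risk (Table 5), but not here.

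**Working it through.** **Step 1. The plan's own precision figure.** Inputs from SAP Section 1.3: n = 300, success rate 50%, two-sided 95% Clopper-Pearson interval. For x successes in n, the lower limit is the 2.5% quantile of Beta(x, n − x + 1) and the upper limit is the 97.5% quantile of Beta(x + 1, n − x). With x = 150 the limits are 44.2% and 55.8%, a half-width of 5.8 points. The stated figure reproduces.

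**Step 2. Trace one participant who dies.**

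- *Which row?* Section 3.3.1.1 takes the withdrawal date from any status except completion: "The date of study withdrawal is the completion or discontinuation date from the DISPOSITION eCRF page, where any participant status other than". Read that way, a death is a withdrawal. If death is coded differently, the catch-all row takes it.
- *Which dose?* Under either row, the last maintenance dose unchanged for 2 consecutive weeks. If 5 mg/day had only just been reached, an earlier stable dose is used.
- *Does a terminal steroid course raise it?* No, not if it is recorded as given for exacerbation or worsening (Section 3.3).
- *Is survival or asthma control checked?* Section 4.2.1.2 has no step for either. Stability refers only to the dose.
- *Is the participant in the denominator?* Yes, through the FAS.

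A last stable dose of 0 mg meets both primary endpoints. A last stable dose above 0 and up to 5 mg/day meets the second only.

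**Step 3. Timing.** A death before Visit 9 carries the dose to both Week 28 and Week 52. A death between Visit 9 and Visit 15 affects Week 52 only.

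**Step 4. Size.** The effect per such death is 1/300 = 0.33 points in the FAS. The documents give no mortality figure. The counts below are therefore assumptions: the number of deaths that would otherwise be scored as successes. The table shows the proportion and 95% limits once these are rescored as non-success (– means not tabulated).

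| Deaths rescored | From 150/300 | From 240/300 |
|---|---|---|
| 0 | 50.0% (44.2 to 55.8) | 80.0% (75.0 to 84.4) |
| 1 | 49.7% (43.9 to 55.5) | – |
| 3 | 49.0% (43.2 to 54.8) | 79.0% (74.0 to 83.5) |
| 6 | 48.0% (42.2 to 53.8) | – |
| 9 | 47.0% (41.2 to 52.8) | 77.0% (71.8 to 81.6) |

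The shift runs from 0.3 points (1/300) to 3.0 points (9/300).

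Not every death would be a success. If 6 participants died and half had a qualifying stable dose, in line with the planned 50% rate, 3 would be rescored: 3/300 = 1.0 point.

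**Step 5. Subgroups.** Each of the two low-eosinophil screening strata is planned at 10% of 300 = 30 participants, so one such death moves the proportion by 1/30 = 3.3 points. In a subgroup of 50, the smallest size in SAP Table 2, it moves by 1/50 = 2 points.

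**The case against.** Several counter-arguments have force.

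- *Table 4 is exhaustive.* True. The withdrawal and catch-all rows between them cover every participant, so a reader who infers that the plan has no rule for death goes too far. Death is unnamed, and a default row handles it.
- *The coding of death is inferred.* Also true. Section 3.3.1.1 lists date of death and date of study withdrawal as separate terms, and the eCRF coding is not shown. The result does not depend on it, because both candidate rows carry a stable dose forward.
- *A fatal asthma attack is itself loss of control.* By the footnote to SAP Table 1 it normally would be. But the derivation never applies that definition, and the definition would not reach a death from another cause. The absence of such a step also affects survivors. That is a wider matter, and a death row does not repair it.
- *The withdrawal row asks for stability at the time of withdrawal.* On one reading, a participant who was unstable at death has no qualifying dose and, with no imputation and an FAS denominator, is a non-success. The SAP does not settle this, which is a further reason to state a rule.
- *Deaths are reported elsewhere.* Fatal serious adverse events are tabulated (Section 4.6.2.2) and withdrawals are shown with reasons (Section 4.1.1.2). This makes deaths visible but does not change the primary numerator.
- *The exacerbation-free endpoint is not a precedent for death.* Section 4.2.4.2 sets out who cannot count as a success there: "Participants who did not complete the planned treatment period or initiate another biologic during the planned treatment period are defined as not having a successful". That fails every non-completer and every biologic starter. It does show that one death can be a failure there and a success on the primary endpoints.

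**Conclusion.** The point holds as a defect in the stated rule: it can turn a death into a primary success, and no planned analysis reverses that. It does so only if the last dose held for 2 weeks was 0 mg or at most 5 mg/day, and only for the visits that follow the death. A reader might infer that every death during the taper is scored a success at both time points. The documents do not support that, because of the 2-week condition and the timing in Step 3.

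Nor do they support a claim that the primary results are materially inflated. The effect is 0.33 points per such death in the FAS, mortality is not stated, and the total is probably small against 5.8 points. The study tests no hypothesis and has no comparator. The case for change rests mainly on what the endpoint means, and secondarily on small strata, where a single death moves the estimate by about 3 points.

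**What to change.** 1. In SAP Sections 1.1 and 4.2, name death before the visit of interest as an intercurrent event. Give it a composite strategy: non-success for both primary endpoints and for the 50%-or-more reduction.
2. Add a matching row to Table 4, worded to apply however death is coded on the DISPOSITION page. A participant who has died has no visit date, so tie the row to the scheduled day: first dose + 196 days for Week 28 and + 364 days for Week 52, as Section 4.2.13.2 already does for censoring.
3. In the categorised-reduction table and the shift tables, show deaths on a separate line headed Died. Do not place them in Category 5, which means no change or an increase and would misdescribe someone who had reduced.
4. Make the same change in Protocol Section 3 and Table 13, or record it in SAP Section 2, which currently reports no difference from the protocol.

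This needs no new data: the work is one intercurrent event, one row and one display line. The downside is that the reported success proportions may be slightly lower. They cannot rise.
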